#### 8.4 Clinical Safety Laboratory Assessments

Hematology, serum chemistry, coagulation and urinalysis data will be collected as specified in the study schedule of Assessments (Appendix A). Hematological toxicities will be assessed according to NCI-CTCAE V5.0 AE grading.

All laboratory results will be presented in the listings. Abnormal laboratory values with their clinical significance status will be presented in a listing. The laboratory tests cut off values are presented in Appendix B.

**Table 2: Clinical Laboratory Tests**

Hematology	Serum Chemistry
Hematocrit (Hct)	Albumin
Hemoglobin (Hgb)	Alanine aminotransferase (ALT)
Platelet count	Aspartate aminotransferase (AST)
	Alkaline phosphatase (ALP)

Sponsor: Sensi Biotherapeutics

Protocol: SNS301-2-2

Red blood cell (RBC) count	Blood Urea Nitrogen (BUN) or Urea
White blood cell (WBC) count	Bicarbonate or Carbon dioxide (CO 2 )
Neutrophils	Creatinine
Lymphocytes	Creatine phosphokinase (CPK)
Eosinophils	Electrolytes (Na, K, Mg, Cl, Ca, P)
Monocytes	Glucose (either fasting or non-fasting)
Basophils	Lactate dehydrogenase (LDH)
Other cells, if any	Total bilirubin (direct bilirubin if elevated)
Platelets	Total protein
Thyroid	Urinalysis
TSH, T3 and FT4	Specific gravity
Coagulation	pH
International normalized ratio/INR	Glucose
Activated partial thromboplastin time (PTT)	Protein
Other anticoagulant monitoring (if required)	Ketones
HIV screen (at screening, if indicated)	Blood
Hepatitis screen (at screening, if indicated)	Microscopic exam, if abnormalities
HPV/EBV screen (at screening, if unknown)	
Pregnancy test	

The following summaries will be presented for Clinical Laboratory tests:

- Overall values by time point utilizing continuous descriptive statistics for each study stage.
- For categorical parameters, the n and percentage will be displayed for each study stage.
- The change from baseline to each time point for continuous parameters.
- Frequencies and percentages for the shifts in these categories (i.e., low to normal, low to high, high to low, etc.) from baseline to each post-treatment assessment time point. For each continuous laboratory (hematology and chemistry) parameter, results will be categorized as low, normal, or high based on the laboratory normal ranges. Percentages for the shift tables will be calculated based on the number of subjects who had results for both baseline and the corresponding post-treatment assessment time point.

Sponsor: Sensi Biotherapeutics

Protocol: SNS301-2-2

## 8.5 Urinalysis

Urinalysis includes specific gravity, pH, glucose, protein, ketones, blood, RBC, WBC, Casts, and a microscopic exam if abnormal results are noted.

Summaries will be presented by cohort.

- Categorical urinalysis variables (Glucose, Blood, Protein, Ketones, RBC, WBC, Casts) will be summarized by number and percentage (n(%)) of subjects.
- The urine pH and specific gravity will be summarized using descriptive statistics (n, mean (SD), median, Min and Max).

## 8.6 Thyroid Function

Thyroid function tests will be performed at screening and every 6 weeks thereafter.

- TSH, T3 and FT4 data will be summarized using descriptive statistics (n, mean (SD), median, Min and Max).

## 8.7 Coagulation and Anticoagulation Levels

Anticoagulant specific drug and/or anticoagulant factor Xa levels will be obtained from patients receiving anticoagulation therapy at Screening, Day 0, Week 3, Week 6, Week 9, Q6W until Week 45 , thereafter Q12W .

- aPTT, INR, PT, TT and Xa data will be summarized using descriptive statistics (n, mean (SD), median, Min and Max).

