RECIST/iRECIST	X		Q6w from Day 0 until ~12 months, thereafter Q12w						
Hematology ^m	X	X ^f	X ^f	X ^f	X ^f	X ^f		X	
Serum Chemistry ⁿ	X	X ^f	X ^f	X ^f	X ^f	X ^f		X	
Coagulation Panel (aPTT, INR)	X								
Urinalysis ^o	X			X			X	X	
Pregnancy ^p	X	X	X	X	X	X		X	X
TSH, T3 and Free T4 ^q	X			X			X		
CPK	X							X	
HPV/EBV, if unknown	X								
PDL-1	X								
Blood samples for immunology assessments ^r		X	X	X	X	At week 12, then Q6 weeks until Week 36 and Q12w thereafter as well as at disease progression			
Tumor specimen	X			X		Up to 2 optional biopsies and at disease progression			
Adverse Events	X	X	X	X	X	X		X	X
Pembrolizumab ^u		X	X	X	X	X			

SNS-301 ^v		X	X	X	X	After week 9, Q6w for 6 more doses (week 45), thereafter Q12w until PD or 24 months if no PD		
Survival and new anti-cancer therapy follow-up ^w								X

Note: Assessments scheduled on the days of study treatment should be performed before the study treatment unless otherwise noted.

^a Written informed consent can be obtained up to 28 days prior to Day 0 and is required for performing any trial-specific tests or procedures. However, tumor tissue collection (archived or fresh) can exceed 28 days to ensure that sufficient time is available for obtaining the requested sample for trial purposes. Additionally, a pre-screening informed consent is available to obtain archived tumor tissue prior to the study's primary consent. Results of standard-of-care tests or examinations performed prior to obtaining informed consent and within 28 days prior to Day 0 may be used for screening assessments rather than repeating such tests. Screening labs (CBC and chemistry) may be used for Day 0 if they are within 10 days of Day 0.

^b Patients who discontinue early from study treatment (i.e., progression, adverse event, etc.), will be asked to return to the clinic within 30 days after the last dose for a treatment discontinuation visit.

^c Cancer history includes stage, date of diagnosis, and prior anti-tumor treatment. Previous progression data should be collected as well. Demographic information includes sex, age, and self-reported race/ethnicity. HPV, EBV, reproductive status and smoking/alcohol history should also be captured.

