^d A complete physical exam will include head, eyes, ears, nose, throat and cardiovascular, dermatological, musculoskeletal, respiratory, gastrointestinal and neurological systems. Height and weight will also be collected. Any signs and symptoms, other than those associated with a definitive diagnosis, should be collected at baseline and during the study.

^e A targeted, symptom-directed exam will be performed, as clinically indicated.

^f ECOG performance status, targeted physical exam, and local laboratory assessments may be obtained \leq 72 hours before each dosing visit.

^g Patients should be tested for HIV locally prior to the inclusion into the trial only based on investigator's clinical suspicion for HIV infection and HIV-positive patients will be excluded from the clinical trial. Hepatitis B surface antigen, anti-HBc antibody, anti-HBs antibody, and Hepatitis C antibody immunoassays should be tested only per investigator's clinical suspicion during screening and tested locally. In patients who have positive serology for the anti-HBc antibody, HBV DNA should be tested prior to Day 0.

^h Concomitant medications include any prescription medications or over-the-counter medications. At screening, any medications the patient has used within the 7 days prior to the screening visit should be documented. At subsequent visits, changes to current medications or medications used since the last documentation of medications will be recorded.

ⁱ Specific anticoagulant drug and/or anticoagulant factor Xa levels will be obtained only on patients receiving anticoagulant therapy. Drug levels will also be obtained at any time of clinical bleeding. Traditional testing methods can be used for warfarin, heparin (e.g., PT/INR, aPTT, TT). Novel oral anticoagulants may require anticoagulant factor Xa levels or anticoagulant drug specific level testing. See sections Concomitant Medications & Guidance for Investigators for Patients on Anti-coagulants for additional information.

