9.2.14.4 Concomitant Medications

Concomitant medications include any prescription medications or over-the-counter medications. At screening, any medications the patient has used within the 7 days prior to the screening visit should be documented. At subsequent visits, changes to current medications or medications used since the last documentation of medications will be recorded. See Section [Prohibited Medications or Treatments During Study](#) for a list of prohibited medications.

Patients who are receiving anticoagulants will have anticoagulant specific drug level and/or anticoagulant specific factor X α levels obtained at baseline, at each administration of SNS-301, and at the end of study visit to ensure that these levels remain within therapeutic range throughout the duration of the trial. In the event of clinically noted bleeding, these tests will be obtained at the time of bleeding as well. Investigators should use tests routinely used in clinical practice to monitor patients receiving Warfarin, Heparin and/or Low Molecular Weight Heparins, along with the monitoring schedule provided above. Should there be two individual events of SNS-301 interruption for the same patients, then SNS-301 will be discontinued after consultation with the Medical Monitor and Study Sponsor. Clinical management and further workup of the coagulation pathway disturbance will be at the discretion of the investigator.

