Adverse events of special interest (AESI) are required to be reported by the investigator to the Sponsor immediately (i.e., no more than 24 hours after learning of the event; see Section [Adverse Event Reporting](#) for reporting instructions).

AESI s should be reported to:

Global Safety and Pharmacovigilance, Advanced Clinical

Email: [contact]

9.3.11 *Guidance for Investigators for Patients on Anti-coagulants*

Based on the preclinical data and the role of ASPH in post-translational modification of proteins involved in the clotting and anticoagulant pathways (Factors VII, IX, X , Protein C), there may a potential for abnormal coagulation with SNS-301. Should there be a clinically significant AE or SAE recorded, such as clinically noted bleeding, administration of SNS-301 will be held until the AE/SAE returns to baseline. Should there be two individual events of SNS-301 interruption for the

same patient, then SNS-301 will be discontinued after consultation with the Medical Monitor and Sponsor. Clinical management and further workup of the coagulation pathway disturbance will be at the discretion of the treating physician.

9.3.12 *Reporting of Pregnancy*

If pregnancy occurs in a female patient, or female partner of a male patient while the patient is on treatment or until six months after the last dose, the sponsor will be notified within 24 hours of learning of the pregnancy. The pregnancy will be followed until birth or termination. Abnormal pregnancy outcomes (e.g., spontaneous abortion, fetal death, stillborn, congenital anomalies, ectopic pregnancy) are considered SAEs.

Pregnancy should be reported to:

Global Safety and Pharmacovigilance, Advanced Clinical

Email: [contact]

9.3.13 *Time Period and Frequency for Event Assessment and Follow-Up*

All AESIs and SAEs, including death due to any cause, that occur during this study and until 90 days after the last dose of study treatment or until the start of a new anti-cancer treatment, whichever comes first, whether or not expected and regardless of causality, must be reported to the Medical Monitor immediately upon discovery of the event, using an SAE Form.

All AEs will be collected from the time of signing the informed consent form until 30 days after the last dose after the last dose of study treatment or until the start of a new anti-cancer treatment, whichever comes first.

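### The pooled aPTT and INR rows in SAP 8.4 and 8.7 move from all patients at screening to anticoagulated patients only, and bleeding adverse events are not grouped (minor)

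*SAP*

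**What the plan says.** The risk: Protocol 9.3.11, citing preclinical data and the role of ASPH in modifying clotting and anticoagulant proteins, says "there may a potential for abnormal coagulation with SNS-301". Clinically noted bleeding is its example.

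The measurements: in both pembrolizumab schedules of Protocol Table 1, and in SAP Appendix A, the row "Coagulation Panel (aPTT, INR") has a single mark, at screening. Footnote i of Table 1 covers the repeated tests: "Specific anticoagulant drug and/or anticoagulant factor Xa levels will be obtained only on patients receiving anticoagulant therapy". It adds "Traditional testing methods can be used for warfarin, heparin (e.g., PT/INR, aPTT, TT"), and "Drug levels will also be obtained at any time of clinical bleeding".

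The analysis: SAP 8.7 opens with the monitored patients: "Anticoagulant specific drug and/or anticoagulant factor Xa levels will be obtained from patients receiving anticoagulation therapy at Screening, Day 0, Week 3", and later visits. It then says "aPTT, INR, PT, TT and Xa data will be summarized using descriptive statistics (n, mean (SD), median, Min and Max"). It names no time point, analysis set or split. SAP 8.4 also covers coagulation (INR and PTT are in its Table 2) and plans values by time point for each study stage, plus change from baseline. SAP 3.1 splits summaries by cohort and overall, and SAP 9.4 rules out subgroup analysis. In SAP 8.3 adverse events are tabulated by organ class and preferred term, and the only event of special interest is a systemic administration site reaction.

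**The concern.** A table of values by time point is read down its rows. For aPTT and INR the screening row holds every patient and each later row holds only those on anticoagulants, whose values may be raised by their treatment. The row means can therefore climb although no patient has changed. Nothing in the SAP separates the two groups, or separates warfarin, heparin and newer oral agents.

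A second gap sits beside it. Patients not on anticoagulants have no scheduled coagulation test after screening, so no re-tabulation of laboratory data can show the named risk in them. What remains is mainly their adverse events. Bleeding at different sites is coded to different preferred terms, so a modest excess could be spread over several lines with no total.

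Safety is a primary objective. The stake is a coagulation display that could suggest an effect that is not there, and no single count for the risk in the patients who are not tested.

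**Working it through.** **1. Who contributes to each row** (Protocol Table 1 and footnote i, inclusion criterion 9, SAP Appendix A)

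| Test | Screening | Day 0 and later scheduled visits |
|---|---|---|
| aPTT, INR | all patients | anticoagulated patients only |
| PT | not in the all-patient panel; an alternative to INR in eligibility | anticoagulated patients only |
| TT | anticoagulated patients only | anticoagulated patients only |
| Drug or Xa level | anticoagulated patients only | anticoagulated patients only |

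The scheduled population changes for aPTT and INR. It does not change for TT or Xa.

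**2. When the change occurs.** Monitored patients are also sampled on Day 0, and the note under Table 1 places assessments on treatment days before study treatment. The jump therefore falls between screening and pre-dose Day 0. Rows from Day 0 onward come from the monitored group.

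**3. How large it could be.** The documents give no share of anticoagulated patients, no mix of agents and no INR values, so everything in this step is assumed. Let f be the share anticoagulated, w their mean INR and u the mean INR of the others, with no change in any patient.

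- Screening mean = f·w + (1 − f)·u
- Later mean = w
- Apparent rise = w − [f·w + (1 − f)·u] = (1 − f)(w − u)

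With u = 1.0, w from 2.0 to 3.0 and f from 5% to 30%:

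| f | w | Screening mean | Later mean | Apparent rise |
|---|---|---|---|---|
| 0.30 | 2.0 | 0.60 + 0.70 = 1.30 | 2.00 | 0.70 |
| 0.10 | 2.5 | 0.25 + 0.90 = 1.15 | 2.50 | 1.35 |
| 0.05 | 3.0 | 0.15 + 0.95 = 1.10 | 3.00 | 1.90 |

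Split by anticoagulant use, or taken as change within patient, the rise is 0. The value 0.70 is not a floor: if the monitored patients' INR is close to u, the pooled rise also goes to 0.

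**4. How many patients have on-treatment tests.** Protocol 10.2 states about 95% probability of seeing at least one event of 5% incidence among 60 patients. This reproduces: 1 − 0.95^60 = 95.4%. A laboratory abnormality can be seen at scheduled visits only in monitored patients. With the same assumed shares these number 60 × 0.05 = 3 to 60 × 0.30 = 18, giving 1 − 0.95^3 = 14.3% to 1 − 0.95^18 = 60.3%.

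**5. Sampling schedules set side by side** (after Week 9)

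- SAP 8.7: six-weekly from Week 9 to Week 45, then 12-weekly.
- SAP Appendix A and the Protocol three-weekly schedule: Week 12, then six-weekly to Week 45, then 12-weekly. Six-weekly steps from Week 12 reach 42 and 48, not 45.
- Protocol six-weekly schedule: after Week 12, six-weekly to Week 42, then 12-weekly.
- Protocol 9.2.14.4: baseline, each SNS-301 administration, and the end of study visit.

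These define different rows for the same table.

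**The case against.** The case against is substantial and much of it stands.

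- SAP 8.7 names no visits, and its opening sentence is about anticoagulated patients. It can be read as limited to them throughout, with no shift. True, but it does not say so, and the time-point table in 8.4 carries no such limit.
- The change from baseline in 8.4 is within patient, so the change in who is measured does not affect it. The n in each row would show the fall in numbers, and 8.4 lists all laboratory results, with abnormal values marked for clinical significance. All of this stands and limits the harm.
- Adverse events are already tabulated by organ class, term and severity in a single-arm trial of about 60 patients. A bleeding group adds convenience more than new data. That is fair, but for patients without tests it is the most useful summary available.

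A reader might also infer more than the documents support:

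- That all five tests are affected. Only aPTT and INR are.
- That a rise from screening to Week 3 could not be told from a drug effect. The pre-dose Day 0 value in monitored patients allows that comparison.
- That this is the only mechanism-based harm the protocol names. Protocol 3.3 also raises uterine implantation.
- That the hemoptysis event in Protocol 3.1.2 is evidence of the risk. Its relationship to treatment is not stated.
- That counts outside the therapeutic range can be made from existing data. Protocol 9.2.14.4 says levels are taken "to ensure that these levels remain within therapeutic range throughout the duration of the trial", but neither document defines a range or says that one is recorded.

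**Conclusion.** The point holds in limited form and is minor. For aPTT and INR, the time-point summaries in SAP 8.4, and 8.7 unless it is read as confined to anticoagulated patients, put all patients in the screening row and only anticoagulated patients in later rows. The means can then rise without any SNS-301 effect. This is a risk of misreading, not a certain false finding, and it does not extend to TT, Xa or the within-patient change.

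The size cannot be derived from the documents. The INR rise of 0.70 to 1.90 rests wholly on the assumed shares and INR values, and on monitored patients having INRs of 2.0 to 3.0. It shows the mechanism and is not an estimate.

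Two related points rest on the documents alone: patients not on anticoagulants have no scheduled coagulation test after screening, and SAP 8.3 plans no grouped bleeding count. The sampling schedules also disagree.

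**What to change.** 1. In SAP 8.4 and 8.7, report screening aPTT and INR for all patients in a separate table, by baseline anticoagulant use.
2. Limit post-screening coagulation summaries to anticoagulated patients. Show paired change from the patient's own pre-dose value, and state whether that is screening or Day 0. Split by agent class where numbers allow; otherwise list. List patients who start or switch an anticoagulant after Day 0. Keep unscheduled samples drawn at bleeding out of the scheduled-visit rows.
3. In SAP 8.3, add one table of a prespecified group of bleeding and coagulation adverse events in the Safety Analysis Set, by cohort and baseline anticoagulant use.
4. In SAP 9.4, note these splits as exceptions to the rule against subgroups.
5. Do not add therapeutic-range counts unless a range is recorded for each patient.
6. Reconcile the sampling schedules in SAP 8.7, SAP Appendix A, the two Protocol Table 1 schedules and Protocol 9.2.14.4, so that the visit rows are defined.

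Items 1 to 4 use laboratory, medication and adverse event data already planned, with no new samples. The cost is SAP wording, a little more table work and small cells: 3 to 18 monitored patients out of 60 under the assumed shares, before any split by agent or cohort. None of this provides on-treatment coagulation values for patients not on anticoagulants.

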## 8.8 Electrocardiograms

12-Lead ECG will be completed at screening/baseline visit.

- The overall assessment categories (Normal, Abnormal; not clinically significant, Abnormal; clinically significant) will be summarized.
- ECG data will be presented in a data listing.

## 8.9 Eastern Cooperative Oncology Performance Status

ECOG performance will be completed at screening/baseline, Cycles 1,2,3,4 and every 3 weeks thereafter, and at the discontinuation visit on a 6-point scale from grade 0-5 as presented in Appendix C.

Sponsor: Sensi Biotherapeutics

Protocol: SNS301-2-2

- ECOG PS assessments will be summarized overall as categorical variables by time point utilizing descriptive statistics.

## 8.10 Vital Signs and Weight

Vital signs and Weight will be taken at various timepoints: Baseline/Screening visit, Cycle 1 Day 0, Cycle 2 Week 3, Cycle 3 Week 6, Cycle 4 Week 9, Every 3 weeks, and at the discontinuation visit. Height will only be taken at baseline/screening visit.

- Descriptive statistics will be presented for each timepoint.
- Descriptive statistics will also be presented for the changes in vital signs from baseline to each post-treatment assessment time point.

## 8.11 Physical Examinations

A full physical examination will be performed at screening/baseline. There will also be targeted physical examinations at these timepoints: Cycle 1 Day 0, Cycle 2 Week 3, Cycle 3 Week 6, Cycle 4 Week 9, Every 3 weeks afterwards and at discontinuation visit.

- Physical exams will be presented in data listings

## 8.12 Pregnancy Testing

Pregnancy testing (when applicable) will be carried out at every visit except the every 6 weekly visits.

- Pregnancy testing results will be presented in data listings

## 8.13 Immunogenicity Assessments

Processing of immunogenicity samples will be performed at Sensei Biotherapeutics or designee. The analyses of these assessments is beyond the scope of this SAP.

## 8.14 ASPH Immunohistochemistry (IHC) Assay

ASPH testing will be done by immunohistochemistry on either fresh or archival tumor tissue. Additional preparation of the slides will be performed at Sensei Biotherapeutics or designee. Staining intensity and distribution of ASPH levels will be evaluated according to the following scale:

- Negative =0;
- Moderate =1+
- Strong=2+

Sponsor: Sensi Biotherapeutics

Protocol: SNS301-2-2

- Very strong immunoreactivity = 3+

Preparation of the slides will be performed at Sensei Biotherapeutics or designee. The analyses of these assessments is beyond the scope of this SAP.

## 9. STATISTICAL/ANALYTICAL ISSUES

### 9.1 Handling of Dropouts or Missing Data

All available data will be presented on the data listings as collected.

Algorithms for imputing partial or missing dates related to AEs and prior/concomitant medications are shown below.

Table 3      Imputation Rules for Partially Missing Dates

Variable	Missing Day	Missing Day, Month	Missing Day, Month, Year
Date of Last Therapy/Date of Initial Diagnosis	Assign 1	Assign January 1 if prior to date of informed consent, otherwise use date of informed consent	Missing (do not impute)
Adverse Event/Medication Start Date	Assign first day of month unless it is the month of first dose of study medication. Otherwise, assign date of first dose of study medication.	Assign January 1 unless the year is year of first dose of study medication Otherwise, assign date of first dose of study medication.	Assign date first dose of study medication.
Adverse Event/Medication End Date	Assign the last day of the month or end of study date, whichever is earlier.	Assign December 31 or end of study date, whichever is earlier.	If ongoing, end date is missing. Otherwise, assign end of study date.

Every effort to re-contact the patient lost to follow-up patients will be made, to identify the reason why he/she failed to attend the visit, and to determine his/her health status, including at least his/her vital status. Data from lost to follow-up subjects to the date of last recorded contact will be included in the analyses.

Non-evaluable patients will be replaced.

Sponsor: Sensi Biotherapeutics

Protocol: SNS301-2-2

